#### 6.2.4 Confidence intervals for occurrence rates of AEs and SAEs

The occurrences of AE or SAE by preferred term will be modeled to follow approximately a Poisson process with constant intensity  $\theta$ . The rate parameter  $\theta$  will be estimated as  $\lambda=D/T$ , where

- Numerator ( $D_i$ ) = total number of events (AE or SAEs by PT) observed within the cohorts and overall ( $i=1,2,3$  for cohort 1, 2 and overall, respectively). PTs which were reported more than once on the same day (within the same patient) will be counted as one event under the highest severity grade.
- Denominator ( $T_i$ ) = The sum of exposure time  $t$  across all patients in group  $i$  per 100 patient years. For a single patient the exposure time  $t$  is derived as:  $t = (\text{minimum date of (last dose + 28 days, last contact day, analysis cutoff day)} - \text{date of first dose during study} + 1) / 365.25$ . The sum of the exposure time of all patients in group  $i$  will be divided by 100 to obtain the exposure time per 100 patient years.
- Note: the analyses of safety and tolerability assessments will concentrate on the on-treatment period, defined to be the period from Day 1 to 28 days after last dose of pasireotide s.c. i.e. the exposure period for  $T_i$  is accordingly adjusted.

Conditionally on  $T$ , an exact  $100*(1-\alpha)\%$  confidence interval for a Poisson variable with parameter  $\theta*T$  and observed value  $D$  can be obtained based on (Garwood, 1936), from which an exact  $100*(1-\alpha)\%$  confidence interval for  $D/T$  will be derived as follows (Sahai, 1993; Ulm, 1990):

$$\text{Lower confidence limit } L = \frac{0.5c_{\alpha/2,2D}}{T} \quad (\text{in SAS: } (0.5*\text{cinv}(\alpha/2,2*D(i))/T(i))$$

$$\text{Upper confidence limit } U = \frac{0.5c_{1-\alpha/2,2D+2}}{T} \quad (\text{in SAS: } (0.5*\text{cinv}(1-\alpha/2, 2*D(i)+2)/T(i)) \text{ for } i=1,2,3 \text{ and } D(i) > 0 \text{ and } 0 \text{ otherwise,}$$

where  $c_{\alpha,k}$  is the  $\alpha$ th quantile of the Chi-square distribution with  $k$  degrees of freedom.

Garwood, F. 1936. Fiducial limits for the Poisson distribution. *Biometrika*. 28(3/4):437-442

Ulm, K. 1990. A simple method to calculate the confidence interval of a standardized mortality ratio. *American Journal of Epidemiology* 131(2):373-375.

Sahai, H. and Khurshid, A. (1993a). "Confidence intervals for the mean of a Poisson distribution: A review", *BiomtrcJ*, 35, 857-867.

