### **Occurrences of AEs and SAEs adjusted for exposure**

The exposure times by cohort is different, therefore, exposure adjusted occurrence rates will aid in the interpretation of differences in the occurrence of AEs/SAEs. Exposure adjusted occurrence rates will be presented (per 100 years of patient exposure), together with 95% confidence intervals. Summaries will be presented for treatment emergent AEs and SAEs.

Confidence intervals will be derived assuming a Poisson process for the occurrence of AEs (SAEs). See Section 5.4 for further details.

Summaries of exposure adjusted occurrence rates will be produced for AEs and SAEs by PT. Only AEs (SAEs) with more than 2 occurrences per preferred term will be displayed.

The analyses on occurrences of AEs and SAEs will be repeated by country.

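### As printed, SAP 6.2.4 sets the upper confidence limit of an AE/SAE rate to 0 when no event is observed; the zero exception belongs to the lower limit

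*SAP*

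**What the plan says.** SAP 6.2.4 treats the occurrences of each preferred term as a process that "will be modeled to follow approximately a Poisson process with constant intensity". The rate is estimated by D/T. D is the "total number of events (AE or SAEs by PT) observed within the cohorts and overall", and T is exposure in units of 100 patient-years. The section names the exact Garwood interval and prints two limits:

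- Lower: L = 0.5·c(α/2; 2D)/T, with no condition attached.
- Upper: U = 0.5·c(1−α/2; 2D+2)/T, for i = 1, 2, 3 and "D(i) > 0 \text{ and } 0 \text{ otherwise".

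Here c(q; k) is the q quantile of the chi-square distribution with k degrees of freedom. Both limits are also given as SAS expressions.

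The use of these rates is set out in SAP 8.4.1, under the heading on occurrences adjusted for exposure: "Exposure adjusted occurrence rates will be presented (per 100 years of patient exposure), together with 95% confidence intervals". Because exposure differs between the cohorts, "exposure adjusted occurrence rates will aid in the interpretation of differences in the occurrence of AEs/SAEs". The display rule is "Only AEs (SAEs) with more than 2 occurrences per preferred term will be displayed", and "The analyses on occurrences of AEs and SAEs will be repeated by country". For the method the reader is told: "See Section 5.4 for further details".

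**The concern.** Observing no event does not show that the rate is zero. It leaves a lower limit of 0 and a positive upper limit that shrinks as exposure grows. The printed rule instead gives 0 to 0 for any exposure, however short, as if every positive rate had been excluded.

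The exception also sits on the wrong limit. At D = 0 the lower formula calls a chi-square quantile with 0 degrees of freedom and needs a rule, but has none. The upper formula is well defined there and needs no exception.

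What is at stake is the comparison for which the SAP introduces these rates. If one cohort has a few events of a term and the other has none, the second cohort's interval collapses to a point and the two look clearly apart. Because the limits are written as code, they may be programmed as they stand. Protocol 6.3 also commits to incidence rates with 95% confidence intervals, so these intervals are a planned output.

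**Working it through.** **Inputs from the documents.** 95% two-sided intervals, so α = 0.05 (SAP 8.4.1); the formulas for L and U and the unit of T (SAP 6.2.4); columns for cohort 1, cohort 2 and overall (SAP 6.2.4).

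**Assumed.** Patient-years per column and the split of exposure between cohorts, which the documents do not give.

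**1. The formulas for D > 0.** On the count scale (limits before division by T):

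| D | 0.5·c(0.025; 2D) | 0.5·c(0.975; 2D+2) |
|---|---|---|
| 1 | 0.0253 | 5.572 |
| 2 | 0.242 | 7.225 |
| 3 | 0.619 | 8.767 |

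Each limit leaves a Poisson tail of 0.025, so for D > 0 the SAP's formulas are the Garwood limits.

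**2. D = 0.** The printed rule gives U = 0. The SAP's own formula gives 0.5·c(0.975; 2)/T = −ln(0.025)/T = 3.689/T. The lower formula has 0 degrees of freedom and returns no value, so L = 0 has to be set by rule. As printed, the upper limit jumps from 0 at D = 0 to 5.572/T at D = 1; by the formula it moves from 3.689/T to 5.572/T.

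**3. Size of the missing upper limit.** U at D = 0, per 100 patient-years:

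| Patient-years in the column (assumed) | T | U by formula | U as printed |
|---|---|---|---|
| 20 | 0.2 | 3.689/0.2 = 18.4 | 0 |
| 50 | 0.5 | 3.689/0.5 = 7.4 | 0 |
| 100 | 1 | 3.7 | 0 |
| 300 | 3 | 3.689/3 = 1.2 | 0 |

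**4. Coverage.** For one column with expected count μ, ignoring the display rule, coverage is the sum of the Poisson probabilities of those D whose interval contains μ. At μ = 0.1, only D = 1 qualifies under the printed rule: 0.1·exp(−0.1) = 0.090. Moving the exception to L adds P(D = 0) = exp(−0.1) = 0.905, giving 0.995.

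| μ | As printed | Exception on L |
|---|---|---|
| 0.1 | 9.0% | 99.5% |
| 0.5 | 37.9% | 98.6% |
| 1 | 61.3% | 98.1% |
| 2 | 84.8% | 98.3% |

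**5. Effect on a cohort comparison.** Assume 50 patient-years in each cohort, with 3 events in one and 0 in the other.

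- First cohort: 3/0.5 = 6.0, with limits 0.619/0.5 = 1.2 and 8.767/0.5 = 17.5.
- Second cohort as printed: 0 (0 to 0).
- Second cohort by formula: 0 (0 to 7.4).

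The printed intervals are separate; the correct ones overlap from 1.2 to 7.4.

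**6. When a zero cell would be shown.** If the display rule is applied within each column, every displayed cell has D ≥ 3 and the faulty branch is never used. If it is applied to the overall count, a term with 3 events in one cohort and none in the other is shown. With equal true rates, independent events and a share p of the exposure in one cohort, the chance that one cohort has none of the D events is p^D + (1−p)^D:

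| Events overall | 50:50 split | 70:30 split |
|---|---|---|
| 3 | 25% | 0.7³ + 0.3³ = 37% |
| 4 | 12.5% | 25% |
| 5 | 6% | 17% |

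For the tables by country, SAP 8.1.2 gives 100 to 200 patients in about 35 countries, an average of 100/35 = 2.9 to 200/35 = 5.7 patients per country. If terms were selected on an overall count there too, zero cells would be common.

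**The case against.** The finding depends on where one trailing clause sits in text read from a PDF. It may have stood beside the lower limit in the source, and the named method and the D > 0 formulas suggest a drafting slip rather than a chosen method. That caution about intent stands. It does not rescue the text: if the clause covers both limits, U is still 0 at D = 0. Only a reading that ties it to L alone would be right, and the printed order does not support that reading.

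The reach is small, and this also stands. The affected cells are zero cells in the cohort or country columns of a descriptive table. The overall column of a displayed term cannot be zero. The primary endpoint is a percentage of patients (SAP 8.4.1), no formal test is planned (SAP 4.1), and a 0 to 0 interval is visibly odd.

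The display rule is worded per preferred term, so a filter on the whole row is its plain reading. This weakens any complaint about ambiguity, but it is also the reading under which zero cohort cells appear.

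Finally, the exposures and splits used above are illustrative, and independence of events is an assumption. SAP 6.2.4 counts repeat events in one patient; such clustering would probably make zero cells more frequent.

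**Conclusion.** The concern holds: the rule is wrong as written. At D = 0 the SAP prints an upper limit of 0, where its own formula and the method it names give 3.689/T, and it leaves the lower limit undefined. Nothing elsewhere in the documents corrects this.

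Severity is minor. The error shows only if zero cells are displayed, which requires the threshold to act on the overall count, and it touches only those cells. The formula result rests on no assumption; the limits in patient-year terms and the zero-cell chances rest on the assumed exposures and splits.

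Two secondary points add no weight. The SAP does not say whether the display count is overall or per column, or how it applies by country. The reference to Section 5.4 is clerical: SAP Section 5 ends at 5.2, and the method is in 6.2.4.

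**What to change.** - In SAP 6.2.4, set L = 0 when D = 0, and compute U = 0.5·c(1−α/2; 2D+2)/T for every D, including 0.
- In SAP 8.4.1, add one sentence saying whether the more-than-2 threshold is applied to the overall count or to each column, and how it works in the tables by country.
- In the same place, change the reference from Section 5.4 to Section 6.2.4.

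The cost is one moved clause, one added sentence and one corrected reference. No new data or analysis is needed. If zero cells are displayed, they will show a positive upper limit in place of 0.

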## 7 ANALYSIS POPULATIONS

### 7.1 RELEVANT PROTOCOL DEVIATIONS

The number and percentage of patients in the FAS with any protocol deviation will be tabulated by the deviation category (as specified in Attachment 9.1) and cohort.

All protocol deviations will be listed.

### 7.2 DEFINITION OF POPULATIONS FOR ANALYSIS

#### 7.2.1 Full Analysis Set

The Full Analysis Set (FAS) comprises all patients who have signed informed consent (or acknowledged an equivalent document) and have been treated with pasireotide s.c. after enrollment into the study.

The full analysis set will be used for all efficacy analyses.

#### 7.2.2 Safety Set

The safety set consists of all patients who have signed informed consent (or acknowledged an equivalent document), have been treated with pasireotide s.c. after enrollment into the study, and have at least one safety assessment after the first dose.

Patients who do not fulfill these criteria will be identified before database lock and presented in a listing.

The safety set will be used for all safety analyses.

## 8 PLANNED ANALYSES

As described in Section 4.1, analyses will be performed every year with the first analysis conducted approximately 12 months after the first patient entered the study.

### 8.1 Analysis of the primary efficacy objective

The primary objective is to evaluate long term safety as assessed by the occurrence of AEs / SAEs.

#### 8.1.1 Primary efficacy endpoint

There is no primary efficacy endpoint in this study.

#### 8.1.2 Statistical hypothesis, model, and method of analysis

The sample size for this study is not based on statistical considerations. It is anticipated that up to approximately 100 sites in about 35 countries will participate in the study. The study will enroll a minimum of 100 patients up to a maximum of 200 patients. The actual sample size may differ from this planned number.

### 8.2 Analysis of secondary efficacy objective(s)

The secondary objective of the study is to evaluate clinical benefit as assessed by the investigator.

#### 8.2.1 Secondary efficacy endpoints

The secondary efficacy endpoints are as follows:

---

1. Proportion of patients with a mean UFC  $\leq$  ULN at 1, 3, 6, 12, 24 and 36 months after enrollment into the study.
2. The absolute and percentage change from baseline in biochemical measures of disease activity (mean UFC, serum cortisol, serum cortisol after dexamethasone, salivary cortisol, ACTH, fasting serum lipid profile (total cholesterol, HDL, LDL)) over time.
3. Proportion of patients achieving normalization of biochemical measures of disease activity (serum cortisol, serum cortisol after dexamethasone, salivary cortisol, ACTH) over time, where normalization refers to being within the upper and lower limit of normal ranges.
4. The absolute and percentage change from baseline in clinical signs and symptoms (blood pressure, body weight, body mass index, waist circumference) over time.
5. The proportion of patients with favorable shift from baseline in clinical symptoms of Cushing's disease over time.
6. The change from the last dose of pasireotide s.c. to 90 days after permanent discontinuation of pasireotide s.c. for patients who discontinue pasireotide s.c. prior to completing 3-year observation period. This change will be evaluated for all available continuous efficacy parameters.
7. The absolute and percentage change from baseline in tumor size over time.
8. The absolute and percentage change from baseline in patient reported outcome questionnaires (Cushing QoL and EURO QoL) over time.

All efficacy analyses will be done for all patients in the FAS and for the two cohorts. And all efficacy analyses except those under 5 will be done for the subgroup patients from German sites. Additionally, the efficacy analyses described under 1, 2, and 3 above will be repeated for the following subgroups of patients:

- Patients treated with monotherapy pasireotide s.c. throughout the study
- Patients treated with a combination of pasireotide s.c. with any other therapy for Cushing's disease throughout the study
- Patients who switched from monotherapy to combination therapy or vice versa at any time during the study

For all continuous efficacy variables (biochemical measures of disease activity, blood pressure, body weight, body mass index, waist circumference, tumor size), a Mixed Effects Repeated Measures Model will also be employed to assess the longitudinal changes in these variables.

Except for the analysis of change from end of treatment to 90 days later, the efficacy analyses will only consider on-treatment values, defined as values assessed before end of treatment + 3 days.

All assessments will be assigned to time windows based on the study day on which the assessment was performed. If there are multiple values within a time window, the assessment closest to the target day of the time window will be used, if not indicated otherwise. Further details including the start and end days of the time windows are available in Appendix 16.1.9 of the CSR.

The continuous efficacy parameters will be also evaluated through a couple of sensitivity analyses: the first will be imputing the worst value at that time window in case of missing data and the second on the patients with the full set of values. The same Mixed Model will be employed for both the analyses.

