7.2.2	Monitoring procedures	39
7.2.3	Recording of data and retention of documents	39
7.2.4	Auditing procedures.....	40
7.2.5	Publication of results.....	40
7.2.6	Disclosure and confidentiality.....	40
7.2.7	Discontinuation of study	40
7.3	Ethics and Good Clinical Practice	41
7.3.1	Institutional Review Board/Independent Ethics Committee.....	41
7.3.2	Informed consent.....	41
7.3.3	Declaration of Helsinki	42
8	References (available upon request).....	43

List of tables

Table 3-1

Suggested schedule of assessments..... 21

List of abbreviations

ACTH	Adrenocorticotrophic Hormone
AE	Adverse Event
AESI	Adverse event of special interest
ALT	alanine aminotransferase
APTT	Partial Thromboplastin Time
AST	aspartate aminotransferase
ATC	Anatomical Therapeutical Chemical
b.i.d.	bis in diem/twice a day
BIPSS	Bilateral Inferior Petrosal Sinus Sampling
CD	Cushing's Disease
CI	Confidence Interval
CRF	Case Report/Record Form
CRH	Corticotrophin-Releasing Hormone
CRO	Contract Research Organization
DS&E	Drug Safety & Epidemiology
ECG	Electrocardiogram
EDC	Electronic Data Capture
ESE	European Society of Endocrinology
FDA	Food and Drug Administration
FPG	Fasting Plasma Glucose
GH	Growth Hormone
GIP	Glucose-Dependent Insulinotropic Polypeptide
GLP	Glucagon-Like Peptide 1
HbA1C	Hemoglobin A1C
ICH	International Conference on Harmonisation
IEC	Independent Ethics Committee
IGF-1	Insulin-like Growth Factor
IRB	Institutional Review Board
LDST	Low-Dose Dexamethasone Suppression Test
LOCF	Last Observation Carried Forward
MedDRA	Medical Dictionary for Drug Regulatory Activities
MRI	Magnetic Resonance Imaging
NYHA	New York Heart Association
PT	Prothrombin Time
QoL	Quality of Life
RAP	Report Analysis Plan
RBC	Red Blood Cells
REB	Research Ethics Board
RMP	Risk Management Plan
s.c.	sub-cutaneous
SAE	Serious Adverse Event
SAP	Statistical analysis plan
SI units	International system of units
SSA	Somatostatin Analogue
TSH	Thyroid Stimulating Hormone
UFC	Urinary Free Cortisol

ULN	Upper Limit Normal
WBC	White Blood Cells
WHO	World Health Organization
γGT	Gamma Glutamyl Transpeptidase

Amendments and updates

Number	Date	Section of study protocol	Amendment or update	Reason
1	20-Sep-2013	Sections 1, 2, 3, 6, 7 and 8	Amendment	Discussion with Health Authorities on data collection in large Cushing disease patient population treated with pasireotide s.c.
2		Sections 3, 6 and 7	Amendment	Modifications for publication of study results
				Update to lists and descriptions of adverse events

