Most patients also develop a high set-point for feedback inhibition of ACTH secretion by cortisol. In addition to the patient's medical history and physical examination, several laboratory tests and diagnostic techniques are available for the diagnosis of Cushing's disease. Twenty four hour urinary free cortisol (UFC) measurements, blood sampling for serum cortisol levels, and the low-dose dexamethasone suppression test (LDDST) are widely used as screening tests for the diagnosis of Cushing's disease ([Newell-Price et al 1998](#)). To distinguish Cushing's disease from other forms of hypercortisolism, a confirmation of a pituitary source of ACTH secretion is needed. This includes an inappropriately normal or elevated plasma ACTH level and evidence of pituitary tumor on magnetic resonance imaging (MRI) scan or confirmed by bilateral inferior petrosal sinus sampling (BIPSS) after corticotrophin-releasing hormone (CRH) stimulation test (evidence of a pituitary source of ACTH). It is generally accepted that if the ratio of adrenocorticotrophin concentration in the inferior petrosal sinuses to peripheral

blood is greater than or equal to 3.0 after CRH stimulation, a diagnosis of Cushing's disease can be made ([Oldfield et al 1991](#)).

Pituitary resection of the adenoma is the current first-line therapy for Cushing's disease, but surgical failure rates are as high as 25-30% even in the hands of the most experienced neurosurgeons. Additionally postoperative recurrence rates are as high as 20% by 5 years ([Bochicchio 1995](#), [Sonino 1996](#)). Surgery is in many cases complicated by hypopituitarism, which requires complicated life-long hormonal replacement therapy necessary to sustain life. Treatment usually focuses on replacing the target hormones rather than the pituitary hormones, and in patients who have multiple axis deficiencies maintenance with multiple replacement hormones can be difficult, and requiring close and constant medical monitoring, and can be expensive ([Swearingen et al 1999](#)).

Irradiation of the pituitary is another option but it may take many years to be effective and it is curative in only 15 to 45% of the cases. In addition, due to its lack of specificity the procedure also often results in hypopituitarism. Furthermore, there is a 1 to 2% risk of development of secondary tumors in the field of radiation over subsequent years ([Orth 1995](#)).

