3.5.2.8 Laboratory evaluations

Mild transient elevations in aminotransferases are observed commonly in patients treated with pasireotide. Rare cases of concurrent elevations in ALT greater than 3xULN and bilirubin greater than 2xULN have also been observed.

Monitoring of liver function is recommended prior to treatment with pasireotide s.c. and after one, two, four, eight and twelve weeks during treatment. Thereafter liver function should be monitored as clinically indicated.

Patients who develop increased transaminase levels should be monitored with a second liver function evaluation to confirm the finding. If the finding is confirmed, the patient should be followed with frequent liver function monitoring until values return to pre-treatment levels. Therapy with pasireotide s.c. should be discontinued in case the patient develops jaundice or other signs suggestive of clinically significant liver dysfunction, in case of a sustained increase in AST or ALT of 5x ULN or greater, or if ALT elevations greater than 3xULN occur concurrently with bilirubin elevations greater than 2xULN. Following discontinuation of treatment with pasireotide s.c. patients should be monitored until resolution.

As the pharmacological activity of pasireotide s.c. mimics that of somatostatin, inhibition of pituitary hormones other than ACTH cannot be ruled out. Monitoring of pituitary function (e.g. TSH/free T₄, GH/IGF-1) before and periodically during pasireotide s.c. therapy should therefore be considered, as clinically appropriate.

Available data on the following laboratory parameters will be collected in this study:

- AST
- ALT
- Alkaline phosphatase
- γ GT
- α -amylase
- Total bilirubin
- WBC
- RBC
- Hemoglobin
- Hematocrit
- Platelets
- Sodium

- Potassium
- Magnesium
- Fasting Plasma Glucose
- HbA1C
- GH
- IGF-1
- TSH
- Free T4
- PT
- APTT

If total bilirubin concentration is increased above 2.0 times upper limit normal (ULN), total bilirubin is recommended to be differentiated into the direct and indirect reacting bilirubin.

All local laboratories contributing to the study should provide the sponsor with a copy of each laboratory's certification and a tabulation of the normal ranges and standard deviations from control values for each of the parameters being evaluated. These laboratory references should be forwarded to the sponsor prior to study start and updated promptly if any information changes during the course of the study.

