### **8.2.1.3 Proportion of patients with normalization of biochemical measures of disease activity**

This analysis will be done for serum cortisol, serum cortisol after dexamethasone, salivary cortisol, ACTH.

For each time window, the number and percentage of patients with normalization of biochemical measures of disease activity will be presented together with corresponding exact

(Clopper-Pearson) 95% CI. For this analysis, a patient is considered to have achieved normalization within a time window if all measurements taken within this window are within the normal range. The proportion will be calculated relative to the number of patients with a value for the respective time point.

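### The two-sided normal-range rule is applied to serum cortisol after dexamethasone, a suppression test, so any lower limit above zero counts the most suppressed patients as not normalised

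*SAP*

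**What the plan says.** SAP 8.2.1, endpoint 3, is the proportion of patients whose biochemical measures normalise, "where normalization refers to being within the upper and lower limit of normal ranges". The rule covers "serum cortisol, serum cortisol after dexamethasone, salivary cortisol, ACTH) over time". Protocol 2.2 and 6.5.1 carry the same two-sided definition for the same four measures.

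SAP 8.2.1.3 puts it into operation: "This analysis will be done for serum cortisol, serum cortisol after dexamethasone, salivary cortisol, ACTH". A patient is normalised in a time window "if all measurements taken within this window are within the normal range". No exception is made for the dexamethasone test. The denominator is the patients with a value at that time point, and the section does not say what happens when a value has no usable limit.

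Mean UFC is handled differently. Endpoint 1 in SAP 8.2.1 uses the upper limit only, and SAP 8.2.1.1 counts patients with a UFC value but no ULN separately.

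On the nature of the test, the protocol's abbreviation list has "Low-Dose Dexamethasone Suppression Test". The Introduction says that UFC, serum cortisol and the "low-dose dexamethasone suppression test (LDDST) are widely used as screening tests", and also that "Most patients also develop a high set-point for feedback inhibition of ACTH secretion by cortisol".

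On reference ranges, Protocol 3.5.2.8 asks local laboratories for "a tabulation of the normal ranges and standard deviations from control values for each of the parameters being evaluated". Neither document gives a range, a cut-off or a direction specific to cortisol after dexamethasone.

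**The concern.** A two-sided range suits a quantity for which both low and high values are abnormal. Cortisol after dexamethasone is not of that kind: dexamethasone is given to drive cortisol down, and the abnormal finding is that it stays up. A lower limit therefore acts against the response that the endpoint is meant to record. Because every measurement in a window must lie inside the range, one strongly suppressed value is enough to make the patient a failure for that window.

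A second error is possible but conditional. If the range attached to the value is the ordinary one for serum cortisol, its upper limit may lie well above the level that separates suppression from non-suppression, and patients who did not suppress could be counted as normalised.

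At stake is whether the reported proportions and their exact intervals for this measure can be interpreted. They are produced by time window, overall, by cohort, for German sites and for three therapy subgroups. With ranges from up to about 100 sites, different kinds of range could be mixed within one proportion.

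**Working it through.** The plan states no figure for this endpoint, so there is nothing to reproduce. The check applies the rule to example values and then counts discordant patients. **All limits and shares below are assumptions in arbitrary units; the documents give none, and none is proposed for use.**

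**Step 1: direction of the rule.** Let v be the cortisol value after dexamethasone, C the level at or below which a patient is suppressed, and L and U the limits applied.
- Plan: normalised if L ≤ v ≤ U.
- Suppression criterion: v ≤ C.

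The two agree for every v only if L = 0 (or there is no lower limit) and U = C. If L > 0, every suppressed value below L is a false failure. If U > C, every value above C that lies between L and U is a false success.

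**Step 2: example values, with C = 50 assumed.**

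| v | Suppressed? | Ordinary-type range 150-600 | Test-specific 20-50 | Test-specific 0-50 |
|---|---|---|---|---|
| 10 | yes | failure (wrong) | failure (wrong) | normalised |
| 30 | yes | failure (wrong) | normalised | normalised |
| 50 | yes | failure (wrong) | normalised | normalised |
| 200 | no | normalised (wrong) | failure | failure |
| 400 | no | normalised (wrong) | failure | failure |
| 700 | no | failure | failure | failure |

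The false failure arises under either range with L > 0. The false success arises only under the ordinary-type range.

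**Step 3: size under an ordinary-type range.** When L > C, no patient can be both suppressed and inside the range. If s is the share suppressed and m the share inside the range:
- true proportion = s; reported proportion = m; discordant = s + m.

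| s | m | Discordant, s + m | Reported minus true, m − s |
|---|---|---|---|
| 20% | 30% | 50% | +10 points |
| 30% | 50% | 80% | +20 points |
| 50% | 30% | 80% | −20 points |

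For the second row with 100 evaluable patients, the exact 95% intervals are 39.8-60.2% around the reported 50% and 21.2-40.0% around the true 30%. The proportion can err in either direction, and if m happened to equal s it would look right although every patient counted in it was misclassified.

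**Step 4: which range would be used?** Protocol 3.5.2.8 asks for ranges for each parameter evaluated, which can be read as including a test-specific one. But the section concerns safety laboratory tests, and its parameter list names no cortisol measure. The documents leave the question open.

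**The case against.** The strongest reply is that the harm turns on a range that the documents do not specify. Serum cortisol and serum cortisol after dexamethasone are listed as separate parameters throughout, and a request for ranges for each parameter could well yield a test-specific range. With such a range no non-suppressed patient counts as normalised, and if it has no lower limit nothing is misclassified. This stands, and it makes the second error conditional. It does not remove the first: the plan states a lower limit, and any such limit above zero penalises the desired result.

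A reader might infer more: that the endpoint as written runs backwards, with nearly all patients misclassified. The documents do not support that. It would need ordinary ranges at every site, and also no patient either above the upper limit or between the suppression level and the lower limit, since both groups are correctly counted as not normalised. Nor would a disagreement with UFC in the same patient prove the point, because two different measures can disagree under any definition.

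It may also be said that the lower limit guards against hypocortisolism, an identified risk in Protocol 3.5.2.3. That is a fair reason to keep it for basal measures. It carries little weight for a value that the test itself has lowered.

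Finally, the consequence is limited. The study is exploratory, the primary endpoint is safety, and UFC control is analysed separately. Changes in cortisol after dexamethasone are also summarised in SAP 8.2.1.2 and modelled under SAP 8.2.1, so the direction of change stays visible. All of this stands and bounds the importance of the point.

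**Conclusion.** The point holds in a bounded form. The plan states a two-sided rule for a suppression test, and neither document contains an exception. Any lower limit above zero counts the most suppressed patients as not normalised. That non-suppressed patients count as normalised is a possibility only, dependent on a range whose upper limit exceeds the suppression level.

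The size cannot be derived from the documents. It runs from zero (test-specific range, no lower limit) to 50-80% discordant in the three assumed ordinary-range scenarios; other shares would give other figures. The conclusion also assumes that a low value is the desired result, which is inferred from the test's name, its screening use and the described feedback defect, and is not stated outright.

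The effect is confined to one of four measures in one of eight descriptive secondary efficacy endpoints. The primary safety endpoint and the sample size, which has no statistical basis, are untouched. The change is worth making because it is cheap and the proportion otherwise has no fixed meaning.

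**What to change.** In SAP 8.2.1 (endpoint 3) and 8.2.1.3, for serum cortisol after dexamethasone only:

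- Define normalization as a value at or below the laboratory's upper limit for that test, with no lower limit.
- State that the ordinary serum-cortisol range is not to be applied.
- Where no test-specific limit is available, treat the limit as missing, leave the value out of the denominator, and show the count by time window, as SAP 8.2.1.1 does for a missing ULN.

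Leave the two-sided rule as it is for serum cortisol, salivary cortisol and ACTH. Because Protocol 2.2 and 6.5.1 contain the same definition, record the departure and its reason in SAP section 3, which at present reports no changes. No numerical cut-off is proposed.

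The cost is a few lines of SAP text, a data query to sites that did not supply a test-specific limit, and fewer evaluable values, hence wider intervals, for this measure.
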